### 5.2.1.5 General dose modifications

Every effort should be made to administer the study drug treatment according to the planned dose and schedule.

In the event of significant toxicity, pembrolizumab dosing should be interrupted, delayed and/or reduced as outlined above in the Table 4. In the event of multiple toxicities, dose modification should be based on the worst toxicity observed.

Dose modifications may occur in three ways:

- Within a cycle: Dosing interruption until adequate recovery followed by dose reduction (if required) during a given treatment cycle.

Azacitidine dosing interruption is not allowed within a cycle unless there is an unexpected and unacceptable toxicity or as defined in Section 5.2.1.5.1.

- Between cycles: The next treatment cycle may be delayed if toxicity from the preceding cycle persists or if specific non-treatment related circumstances arise as defined in Section 5.2.1.4 (other non-treatment related medical/surgical events or logistical reasons).
- In the next cycle: Dose reduction may be required based on toxicities experienced in the previous cycle.

#### **5.2.1.5.1 Dose interruptions/modification for non-hematologic toxicities**

Complications of myelosuppression include infections and bleeding, these may be exacerbated with the use of azacitidine and pembrolizumab treatment. Azacitidine and pembrolizumab treatment may be delayed at the discretion of the investigator, if the subject experiences myelosuppression-associated complications, such as those described below:

- Febrile neutropenia (temperature  $\geq 38.5^{\circ}\text{C}$  and absolute neutrophil count  $< 1,000/\mu\text{L}$ )
- Active uncontrolled viral, bacterial or fungal infection (i.e., requiring intravenous anti-infectives or extensive supportive care)
- Hemorrhage (gastrointestinal, genito-urinary, pulmonary with platelets  $< 25,000/\mu\text{L}$  or any central nervous system hemorrhage)

Treatment may be resumed once the above conditions have improved or have been stabilized with adequate treatment (anti-infective therapy, transfusions).

Azacitidine dose reductions are not recommended other than specified below. If a dose reduction is believed to be necessary for different reasons, a discussion with the Sponsor is required.

Azacitidine dose interruption is not recommended within a cycle unless an unacceptable or unexpected study drug combination related toxicity occurs. Azacitidine and pembrolizumab may have some overlapping toxicities. Dose modifications/interruptions recommendations for non-hematologic toxicities:

- For any grade 3 or higher diarrhea/colitis, hold azacitidine and pembrolizumab. If not immune-related colitis, and if symptoms resolve within 5 days with maximum therapy to  $\leq$  grade 1, may restart azacitidine and pembrolizumab as per schedule. The azacitidine doses can be resumed in the same cycle if no more than a 5 day gap occurred and/or the patient is still likely to have clinical benefit. Pembrolizumab dose will be omitted if delayed for more than 7 days. If not immune-related colitis and but if it requires more than 5 days for toxicities to resolve to  $\leq$  grade 1 then dose reduce azacitidine to  $75\text{ mg}/\text{m}^2 \times 5\text{ day}$  in the next cycle and pembrolizumab to every 4 weeks. For recurrent grade 3 colitis, azacitidine dose can be reduced to  $75\text{ mg}/\text{m}^2 \times 5\text{ days}$  (if

receiving  $75 \text{ mg/m}^2 \times 7 \text{ days}$ ) or to  $50 \text{ mg/m}^2 \times 5 \text{ days}$  (if receiving  $75 \text{ mg/m}^2 \times 5 \text{ days}$ ). Even if not considered immune-related colitis, unless there is an objective reason (i.e., *C diff* infection, viral infection) for recurrent grade 3 colitis, the pembrolizumab will be discontinued for second occurrence of grade 3 colitis. If there is an objective reason, pembrolizumab may be reduced to every 6 weeks (if given every 4 weeks) or to every 4 weeks (if given every 3 weeks).

- For grade 2 diarrhea/colitis that persists more than 3 days hold azacitidine. Pembrolizumab should be held immediately for grade 2 diarrhea/colitis. If not immune-related colitis, and if symptoms resolve within 7 days with maximum therapy to  $\leq$  grade 1, may restart azacitidine and pembrolizumab as per schedule. The azacitidine doses can be resumed in the same cycle if no more than a 5 day gap occurred and/or the patient is still likely to have clinical benefit. Pembrolizumab dose will be omitted if delayed for more than 7 days. If not immune related colitis but if it requires more than 7 days for toxicities to resolve to  $\leq$  grade 1 then dose reduce azacitidine to  $75 \text{ mg/m}^2 \times 5 \text{ days}$  in the next cycle, and reduce pembrolizumab to every 4 weeks. For any recurrent grade 2 diarrhea/colitis lasting more than 7 days, the dose of azacitidine should be reduced to  $75 \text{ mg/m}^2 \times 5 \text{ days}$  (if pt is on azacitidine  $75 \text{ mg/m}^2 \times 7 \text{ days}$ ) or to  $50 \text{ mg/m}^2 \times 5 \text{ days}$  (if pt is on azacitidine  $75 \text{ mg/m}^2 \times 5 \text{ days}$ ). If not immune related recurrent grade 2 diarrhea/colitis but if it requires more than 7 days for toxicities to resolve to  $\leq$  grade 1, dose-reduce pembrolizumab to every 4 weeks (if on every 3 weeks schedule) or every 6 weeks (if on every 4 weeks schedule).
- If unexplained reductions in serum bicarbonate levels to  $< 20 \text{ mEq/L}$  occur, azacitidine dosage should be reduced by 50% on the next course ( $50 \text{ mg/m}^2 \times 5 \text{ days}$ ). Similarly, if unexplained elevations of BUN or serum creatinine occur, the next cycle should be delayed until values return to normal or baseline and the dose of the azacitidine should be reduced by 50% on the next treatment course.

Azacitidine administration should not be interrupted if pembrolizumab dosing is interrupted for toxicity except as defined above or at the discretion of the investigator for any clinical toxicities where ongoing administration of azacitidine is felt to be unsafe (grade 3 or 4 pembrolizumab-related toxicities). The azacitidine doses can be resumed in the same cycle if no more than a 5 day gap occurred, the patient is still likely to have clinical benefit, and the investigator feels that it is safe to restart azacitidine therapy. No dose reduction of azacitidine will be required.

Patients experiencing Grade 3 or 4 toxicities potentially attributable to pembrolizumab should have their pembrolizumab treatment interrupted regardless of when it occurs in the cycle until the toxicity resolves or returns to baseline.

Cycle duration maybe extended beyond 28 days to allow resolution of toxicities related to study treatments (see Table 4). In general, the next cycle of treatment should be restarted when drug-related toxicities resolve to  $\leq 1$ ; even if pembrolizumab cannot be administered (ongoing steroid taper), azacitidine should be restarted. The pembrolizumab can be restarted on any day

of the cycle when the criteria are met for its administration (steroids tapered to the required level) and according to the dose reduction recommendations.

If for unforeseen circumstances (for reasons other than toxicity, eg, emergency surgery, unrelated medical events, or logistical reasons not related to study therapy such as patient vacation, and/or holidays) the patient misses a doses of azacitidine within a cycle, the doses can be resumed in the same cycle if no more than a 5 day gap occurred and the patient is still likely to have clinical benefit. The dose of pembrolizumab within 7 days of surgery will be omitted.

If a treatment delay continues beyond Day 28 of the current cycle, then the day when azacitidine treatment is restarted will be counted as Day 1 of the next cycle.

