## 2.0 TRIAL DESIGN

### 2.1 Trial Design

This is a multicenter, nonrandomized, open-label phase 2 study (with a safety run-in phase) of azacitidine (AZA) 75 mg/m^2 given IV or SQ on days 1-7 every 28 days in combination with pembrolizumab 200 mg given IV every 3 weeks (starting on day 8 of cycle 1). The dose/schedule of AZA selected for this study is FDA approved for patients with MDS/AML. The rationale for pembrolizumab dose/schedule- Section 4.2.2.

We plan to examine two AML patient cohorts:

**Cohort 1:** relapsed/refractory AML.

**Cohort 2:** newly diagnosed AML in older patients ( $\geq 65$  years) not candidates for induction chemotherapy.

Each cohort will be enrolled separately with distinct null hypotheses and statistical plans.

Azacitidine and pembrolizumab have distinct mechanisms of action with no common overlapping toxicities; however, as azacitidine and pembrolizumab have not been tested previously in combination in AML patients, we plan to start enrollment with **Cohort 1 (a safety run-in phase)** and include only relapsed/refractory AML patients excluding those relapsing after allogeneic hematopoietic stem cell transplant (alloHSCT).

**Cohort 1 (a safety run-in phase, 3 + 3 design):** The first three patients will be enrolled and receive planned azacitidine and pembrolizumab in cycle 1 (Section 2.2). If 0 or 1 patient of the first three patients have a DLT (dose limiting toxicity) in cycle 1, we will enroll additional 3 patients to better assess for toxicities. If less than 2 among first 6 patients experiences DLT in the cycle 1-3, we will open enrollment in Cohort 1 for all relapsed/refractory patients including those with prior history of alloHSCT and will also start to enroll patients in Cohort 2. We plan to monitor for DLTs up to the end of cycle 3 as some of immunological side effects associated with pembrolizumab may occur with the delay.

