## 5.2 Trial Treatments

The treatment to be used in this trial is outlined below in Table 1

Table 1. Trial Treatment

Drug	Dose/ Potency	Dose Frequency	Route of Administration	Regimen/Treatment Period	Use
Azacitidine	75 mg/m 	Daily x 7 days	Subcutaneous (SQ) or IV infusion	Day 1 to 7 of each 28 day cycle	Standard
Pembrolizumab	200 mg	Q 3W	IV infusion	*# Starting on Day 8 of Cycle 1	Experimental

- \*Pembrolizumab administration will start on Day 8 of Cycle 1.
- # On days when both agents are administered, azacitidine should be administered before the pembrolizumab. An anti-emetic, preferably a serotonin antagonist, should be administered prior to azacitidine; the individual anti-emetic selected is at the discretion of the investigator.

Trial treatment should begin as close as possible to the date on which treatment is allocated/assigned.

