### 5.2.1.2 Dose Modification (Escalation/Titration/Other)

- Dose modifications will be made based on Common Terminology Criteria for Adverse Events (CTCAE) grading (version 4.0)
- Patients may remain on study and therapy even if one of the agents are discontinued due to toxicity. No more than two dose reductions of any agent is allowed.

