### 5.2.1.5.4 Dose Reductions for Azacitidine and Pembrolizumab

Following dosing interruption or cycle delay due to toxicity, the azacitidine and/or pembrolizumab dose may need to be reduced when treatment is resumed.

Dose reduction of azacitidine and/or pembrolizumab-if necessary, 2 dose levels will be allowed depending on the type and severity of toxicity encountered.

Table 5. Dose Modifications for Azacitidine and Pembrolizumab

Dose modification	Azacitidine	Pembrolizumab
1 st dose reduction	75 mg/m  x 5 days	200 mg every 4 weeks
2 nd dose reduction	50 mg/m  x 5 days	200 mg every 6 weeks

Patients requiring more than 2 dose reductions of azacitidine should permanently discontinue both azacitidine and pembrolizumab, unless patient has achieved response (CR, PR, MLFS, HI, SD) in which case patients may be allowed to continue pembrolizumab only as long as they have ongoing clinical benefit without evidence of significant toxicity or disease progression and up to 2 years.

All dose modifications/adjustments must be clearly documented in the patient's notes and CRF. Once dose has been reduced, all subsequent cycles should be administered at that dose level, unless further dose reduction is required. Dose re-escalation is not allowed.

Once the azacitidine dose has been reduced for a given patient, subsequent cycles should be administered at that dose level. If a patient undergoes two cycles at a reduced dose without recurrent hematologic toxicity, dose re-escalation to the next higher dose level is allowed if the dose was initially reduced for hematologic toxicity. Azacitidine dose re-escalation must be discussed and agreed with the Sponsor. If hematologic toxicity recurs, the patient will have the prior dose reduction re-instituted and will not be eligible for a second round of dose re-escalation.

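### The azacitidine cut for low bicarbonate or raised BUN/creatinine gives no single dose for patients already on a reduced dose, and the plan does not say how a direct drop to the second reduction level counts toward the cap of two

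*Combined protocol and SAP*

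**What the plan says.** Full-dose azacitidine is 75 mg/m2, "given IV or SQ on days 1-7 every 28 days" (Section 2.1). The treatment table in Section 5.2 agrees: "Day 1 to 7 of each 28 day cycle".

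Section 5.2.1.5.1 has two laboratory rules. For an unexplained fall in serum bicarbonate below 20 mEq/L, "azacitidine dosage should be reduced by 50% on the next course ( $50 \text{ mg/m}^2 \times 5 \text{ days", the bracket giving 50 mg/m2 x 5 days. For an unexplained rise in BUN or creatinine, presented as a similar case, the next cycle waits for recovery and "the dose of the azacitidine should be reduced by 50% on the next treatment course". No regimen follows. Neither rule depends on the dose the patient is currently receiving.

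Table 5 in Section 5.2.1.5.4 lists 75 mg/m2 x 5 days as the first azacitidine reduction and 50 mg/m2 x 5 days as the second, with nothing lower. Its lead-in says that "2 dose levels will be allowed depending on the type and severity of toxicity encountered". Section 5.2.1.2 sets the cap: "No more than two dose reductions of any agent is allowed". Under Section 5.2.1.5.4, a patient who needs more than two azacitidine reductions stops both drugs permanently, except that a patient with CR, PR, MLFS, HI or SD may continue pembrolizumab alone.

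**The concern.** A percentage of the current dose and a fixed regimen can be the same instruction from only one starting dose. The bicarbonate rule states both, so once a patient is below that starting dose the sentence gives two answers. The BUN/creatinine rule gives only the percentage, although the protocol otherwise reduces azacitidine by named levels.

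The second difficulty is the count. From full dose the bracketed regimen is Table 5's second reduction, reached in one move. The protocol limits reductions to two and makes stopping both drugs depend on exceeding two, but it does not say whether this move is one reduction or two.

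At stake are the azacitidine dose after a stated safety trigger and the point at which a patient must come off treatment. The trigger is foreseeable: Section 5.5.2.5 lists renal tubular acidosis among azacitidine's toxicities. Differences in how sites read the rule would also add variation in exposure to the regimen under test.

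**Working it through.** **Inputs.** Full dose 75 mg/m2 x 7 days (Sections 2.1 and 5.2). First reduction 75 mg/m2 x 5 days and second reduction 50 mg/m2 x 5 days (Table 5). Bracketed regimen 50 mg/m2 x 5 days and stated cut 50% (Section 5.2.1.5.1).

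**Formulas.** Cycle total = daily dose x days. Cut produced by the bracketed regimen = 1 - (50 x 5)/(current cycle total). Literal half = current cycle total / 2.

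**The plan's own figure, from full dose.** 75 x 7 = 525 and 50 x 5 = 250, so the cut is 1 - 250/525 = 52.4%. A literal half is 262.5, and 250 is 4.8% below it. That is close to the stated 50% and is best read as rounding to an existing level.

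**All three current doses (mg/m2 per cycle).**

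| Current regimen | Cycle total | Literal half | Bracketed regimen | Cut from bracketed regimen |
|---|---|---|---|---|
| 75 x 7 | 525 | 262.5 | 250 | 52.4% |
| 75 x 5 | 375 | 187.5 | 250 | 33.3% |
| 50 x 5 | 250 | 125 | 250 | 0% |

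No literal half equals a Table 5 level, and the last two lie below its lowest level. From 75 x 5, the bracketed regimen is one third higher than a literal half (250/187.5 = 1.33).

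**Daily dose instead of cycle total.** 75 to 50 is 1 - 50/75 = 33.3%, so this measure does not give 50% either. Cycle total is the natural measure here, because Table 5's first step shortens treatment and leaves the daily dose unchanged (1 - 375/525 = 28.6% per cycle).

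**Counting.** Take a full-dose patient moved directly to 50 x 5.

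- Counted by event, one reduction is used and one remains, but Table 5 has no lower level to use it on.
- Counted by level, both are used, and the next reduction required brings in the stopping rule of Section 5.2.1.5.4.

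If bicarbonate falls again in that patient, the bracket leaves the dose unchanged, the percentage calls for a cut, and the stopping rule applies or not according to the count.

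**Comparison with neighbouring rules.** The recurrent diarrhea/colitis rules in Section 5.2.1.5.1 and the hematologic rule in Section 5.2.1.5.3 state the new azacitidine regimen according to the one the patient is on. The bicarbonate and BUN/creatinine rules do not.

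**The case against.** The strongest reply is that the rule works for the patient it was probably written for. A full-dose patient with low bicarbonate has a named regimen, it is a Table 5 level, and it differs from 50% only by rounding. That stands. A reader might infer that the dose is undetermined for every patient who meets these rules; the text does not support that.

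A reader might also call the skipped Table 5 level an error in itself. The lead-in to Table 5, which ties the levels to type and severity of toxicity, can be read as permitting a direct move to the second level. That stands too, but the lead-in does not say how the move counts.

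The twofold gap from 50 x 5 (125 against 250) should not be pressed. A patient who reached 50 x 5 by both Table 5 steps and needs another cut already falls under the discontinuation rule. The case stays open only where the count is in doubt.

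It can be said that the count matters little, because Table 5 has no level below 50 x 5 either way, and that speaking of two dose levels favours counting by level. This narrows the consequence. It does not remove it, because the stopping rule is worded in reductions.

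For BUN/creatinine, carrying the bracketed regimen across from the preceding sentence is reasonable, but the text does not do so, and the conflict for already reduced patients would come with it.

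Section 5.2.1.5.3 asks that any dose reduction be discussed beforehand with the Protocol Chair, and Section 5.2.1.5.4 requires modifications to be documented. The former sits under hematologic toxicity but is worded generally. These controls make divergence between sites possible rather than certain. They give the Chair no rule to apply.

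Finally, Section 5.1.1 records Cohort 1 as complete and Cohort 2 as closed to accrual, so only patients on treatment or retreatment could be affected. Treatment may run 24 months (Section 5.9) with up to a further year on retreatment (Section 7.1.5.5), so this limits the reach of the problem without disposing of it.

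**Conclusion.** The concern holds in a limited form, as an inconsistency in a stated safety rule. Three things are unresolved:

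- For low bicarbonate in a patient already reduced, the percentage and the regimen disagree: 187.5 against 250 mg/m2 per cycle from 75 x 5, and no change at all from 50 x 5, where discontinuation may apply instead if both reductions have been used.
- For raised BUN or creatinine, no regimen is given at any dose level.
- For a direct move from full dose to the second Table 5 level, the number of reductions used is unstated.

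The sizes assume that the cut is measured by cycle total and that patients receive the full planned days. The documents do not show how many patients met either trigger or whether sites acted differently, so a claim that doses did diverge, or that the CR/CRi result was affected, would go beyond them. It is worth correcting because the count bears on when both drugs must stop and the correction is small.

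**What to change.** Reconcile Sections 5.2.1.2, 5.2.1.5.1 and 5.2.1.5.4, including Table 5.

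- For the bicarbonate trigger and for the BUN/creatinine trigger, give one instruction for each current azacitidine dose (75 x 7, 75 x 5 and 50 x 5 mg/m2 x days), as a Table 5 level, an explicit regimen or a reference to the discontinuation rule.
- State whether a direct move from full dose to the second level counts as one or two of the permitted reductions, and use the same unit (levels or reductions) in the cap and in the stopping rule.

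The choice of dose and of stopping rule is for the sponsor's clinicians. The cost is a wording or table change in a protocol amendment, with no new procedures or patients.

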#### 5.2.1.4 Immune Adverse Events Associated with Pembrolizumab

Adverse events (both non-serious and serious) associated with pembrolizumab exposure may represent an immunologic etiology. These adverse events may occur shortly after the first dose or several months after the last dose of treatment. Pembrolizumab must be withheld for drug-related toxicities and severe or life-threatening AEs as per Table 4 below. See Section 5.7.5 for supportive care guidelines, including use of corticosteroids.

Table 4. Dose Modification and Toxicity Management Guidelines for Immune-related AEs Associated with Pembrolizumab

General instructions:
1. Corticosteroid taper should be initiated upon AE improving to Grade 1 or less and continue to taper over at least 4 weeks.

2. For situations where pembrolizumab has been withheld, pembrolizumab can be resumed after AE has been reduced to Grade 1 or 0 and corticosteroid has been tapered. For Grade 3 (excluding alopecia, fatigue) toxicities which are eligible for re-dosing: Increase dose interval to every 4 weeks, and to every 6 weeks with second occurrence. Pembrolizumab should be permanently discontinued if AE does not resolve within 12 weeks of last dose or corticosteroids cannot be reduced to  $\leq 10$  mg prednisone or equivalent per day within 12 weeks.
3. For severe and life-threatening irAEs, IV corticosteroid should be initiated first followed by oral steroid. Other immunosuppressive treatment should be initiated if irAEs cannot be controlled by corticosteroids.

Immune-related AEs	Toxicity grade or conditions (CTCAEv4.0)	Action taken to pembrolizumab	irAE management with corticosteroid and/or other therapies	Monitor and follow-up
Pneumonitis	Grade 2	Withhold	
 
• Administer corticosteroids (initial dose of 1-2 mg/kg prednisone or equivalent) followed by taper
 
	
 
• Monitor participants for signs and symptoms of pneumonitis
 
• Evaluate participants with suspected pneumonitis with radiographic imaging and initiate corticosteroid treatment
 
• Add prophylactic antibiotics for opportunistic infections
 

	Grade 3 or 4, or recurrent Grade 2	Permanently discontinue		

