Diarrhea / Colitis	Grade 2 or 3	Withhold	
 
• Administer corticosteroids (initial dose of 1-2 mg/kg prednisone or equivalent) followed by taper
 
	
 
• Monitor participants for signs and symptoms of enterocolitis (ie, diarrhea, abdominal pain, blood or mucus in stool with or without fever) and of bowel perforation (ie, peritoneal signs and ileus).
 
• Participants with <math>\geq</math> Grade 2 diarrhea suspecting colitis should consider GI consultation and performing endoscopy to rule out colitis.
 

	Grade 4	Permanently discontinue		

				
 
Participants with diarrhea/colitis should be advised to drink liberal quantities of clear fluids. If sufficient oral fluid intake is not feasible, fluid and electrolytes should be substituted via IV infusion.
 

AST / ALT elevation or Increased bilirubin	Grade 2	Withhold	
 
Administer corticosteroids (initial dose of 0.5- 1 mg/kg prednisone or equivalent) followed by taper
 
	
 
Monitor with liver function tests (consider weekly or more frequently until liver enzyme value returned to baseline or is stable)
 

	Grade 3 or 4	Permanently discontinue	
 
Administer corticosteroids (initial dose of 1-2 mg/kg prednisone or equivalent) followed by taper
 
	
Type 1 diabetes mellitus (T1DM) or Hyperglycemia	Newly onset T1DM or Grade 3 or 4 hyperglycemia associated with evidence of $\beta$ -cell failure	Withhold	
 
Initiate insulin replacement therapy for participants with T1DM
 
Administer anti-hyperglycemic in participants with hyperglycemia
 
	
 
Monitor participants for hyperglycemia or other signs and symptoms of diabetes.
 

Hypophysitis	Grade 2	Withhold	
 
Administer corticosteroids and initiate hormonal replacements as clinically indicated.
 
	
 
Monitor for signs and symptoms of hypophysitis (including hypopituitarism and adrenal insufficiency)
 

	Grade 3 or 4	Withhold or permanently discontinue 		

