Hyperthyroidism	Grade 2	Continue	
 
Treat with non-selective beta-blockers (eg, propranolol) or thionamides as appropriate
 
	
 
Monitor for signs and symptoms of thyroid disorders.
 

	Grade 3 or 4	Withhold or permanently discontinue 		
Hypothyroidism	Grade 2-4	Continue	
 
Initiate thyroid replacement hormones (eg, levothyroxine or liothyroinine) per standard of care
 
	
 
Monitor for signs and symptoms of thyroid disorders.
 

Nephritis and Renal dysfunction	Grade 2	Withhold	
 
Administer corticosteroids (prednisone 1-2 mg/kg or equivalent) followed by taper.
 
	
 
Monitor changes of renal function
 

	Grade 3 or 4	Permanently discontinue		

Myocarditis	Grade 1 or 2	Withhold	
 
Based on severity of AE administer corticosteroids
 
	
 
Ensure adequate evaluation to confirm etiology and/or exclude other causes
 

	Grade 3 or 4	Permanently discontinue		
All other immune-related AEs	Intolerable/persistent Grade 2	Withhold	
 
Based on type and severity of AE administer corticosteroids
 
	
 
Ensure adequate evaluation to confirm etiology and/or exclude other causes
 

	Grade 3	Withhold or discontinue based on the type of event. Events that require discontinuation include and not limited to: Gullain-Barre Syndrome, encephalitis		
	Grade 4 or recurrent Grade 3	Permanently discontinue		

1. Withhold or permanently discontinue pembrolizumab is at the discretion of the investigator or treating physician.
 
NOTE:
 
For participants with Grade 3 or 4 immune-related endocrinopathy where withhold of pembrolizumab is required, pembrolizumab may be resumed when AE resolves to <math>\leq</math> Grade 2 and is controlled with hormonal replacement therapy or achieved metabolic control (in case of T1DM).
				

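### Section 5.2.1.5.1 and Table 4 conflict on pembrolizumab for some of the same severe events, and no sentence says which governs

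*Combined protocol and SAP*

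**What the plan says.** Two places in the combined protocol and SAP tell sites what to do with pembrolizumab after a severe toxicity.

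**Section 5.2.1.5.1.** A general sentence covers every grade 3 or 4 toxicity potentially attributable to pembrolizumab. Such patients "should have their pembrolizumab treatment interrupted regardless of when it occurs in the cycle until the toxicity resolves or returns to baseline". The sentence names no exceptions. A separate colitis rule in the same section says "the pembrolizumab will be discontinued for second occurrence of grade 3 colitis". That rule applies even where the colitis is not thought to be immune-related. It has one exception: where an objective cause such as an infection is found, the dosing interval may be lengthened instead.

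**Table 4 (Section 5.2.1.4).** The relevant entries are:
- Hypothyroidism: "Hypothyroidism Grade 2-4 Continue".
- Grade 3 or 4 endocrinopathy where the drug has to be withheld: a note lets it resume at grade 2 or lower once hormonal or metabolic control is reached.
- Colitis: "Diarrhea / Colitis Grade 2 or 3 Withhold", with grade 4 a permanent stop.
- Pneumonitis: "Grade 3 or 4, or recurrent Grade 2" is a permanent stop.
- Nephritis, myocarditis and liver-test events: "Grade 3 or 4 Permanently discontinue".
- General instruction 2, for grade 3 toxicities that qualify for re-dosing: "Increase dose interval to every 4 weeks, and to every 6 weeks with second occurrence".

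Section 5.2.1.4 says to withhold pembrolizumab as Table 4 sets out. Section 5.2.1.5 points back to Table 4 for interruption, delay and reduction. Section 5.9 cites both 5.2.1.4 and 5.2.1.5 as grounds for discontinuation.

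**The concern.** The general sentence and Table 4 overlap. Table 4 covers immune-related events, and the general sentence covers anything potentially attributable to pembrolizumab, so it takes in the grade 3-4 immune-related events of Table 4. Where the two differ, a site needs to know which to follow, and no sentence tells it.

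What is at stake is consistent handling of severe toxicity across the centers of a multicenter trial, including whether a patient is re-exposed. Closed accrual does not remove the issue. Cohort 2 closed on 1/8/2020 and treatment may run for 24 months from first dose, so a patient enrolled shortly before closure could be on drug until about January 2022, after Amendment 8 (October 14, 2020). A second course of up to one year is also possible. The documents do not say how many patients were still on treatment.

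**Working it through.** The point rests on no figure in the plan, so the check sets the two texts side by side for events that both cover.

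1. **Grade 3-4 hypothyroidism.** Section 5.2.1.5.1: interrupt. Table 4: continue. If the event is attributed to pembrolizumab, both cannot be followed. This is a direct conflict.

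2. **Resumption after a grade 3-4 endocrinopathy.** Section 5.2.1.5.1: hold until resolution or baseline. Table 4 note: may resume at grade 2 or lower if controlled. A patient controlled at grade 2 whose baseline was lower may resume under one text and not under the other.

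3. **Second grade 3 colitis, no objective cause.** Section 5.2.1.5.1: discontinue. The Table 4 colitis row says withhold and has no recurrence rule. General instruction 2 moves to a 6-week interval at a second occurrence, but only for toxicities that qualify for re-dosing, and Table 4 does not say whether a second grade 3 colitis qualifies. The table's own stop for "Grade 4 or recurrent Grade 3" sits in the row for all other immune-related events, so it does not reach colitis. Because the Section 5.2.1.5.1 rule applies even when colitis is not thought to be immune-related, it also takes in immune-related colitis, which Table 4 covers. The case is left unsettled.

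4. **Events that Table 4 stops permanently.** These are grade 3-4 pneumonitis, hepatic, renal and myocarditis events, and grade 4 colitis: five listings. The general sentence in Section 5.2.1.5.1 has no permanent-stop branch. The two can be combined as hold first, then apply Table 4, but the sentence does not say that.

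5. **Where they agree.** Both hold pembrolizumab for a first grade 3 colitis. Both also hold it for new type 1 diabetes, or grade 3-4 hyperglycemia with beta-cell failure, where the event is grade 3-4 and attributed to the drug.

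6. **Is there a rule of precedence?** Sections 5.2.1.4, 5.2.1.5 and 5.9 contain none. Nor can one be inferred from strictness. Table 4 is the more restrictive text in item 4, and Section 5.2.1.5.1 is the more restrictive in items 1 and 2 and on its face in item 3.

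**Side check on the stopping rule.** Section 8.2.2.1 uses a beta(0.5, 2) prior and stops when the posterior probability of a risk above 0.20 is at least 0.70. With x removals among n patients, Pr = 1 − F(0.2; 0.5 + x, 2 + n − x), where F is the beta distribution function. All eight printed values reproduce:

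| n | x at boundary | Pr | Pr at x − 1 |
|---|---|---|---|
| 5 | 2 | 0.770 | 0.426 |
| 10 | 3 | 0.715 | 0.443 |
| 15 | 5 | 0.852 | 0.684 |
| 20 | 6 | 0.823 | 0.664 |
| 25 | 7 | 0.800 | 0.649 |
| 30 | 8 | 0.781 | 0.637 |
| 35 | 9 | 0.766 | 0.628 |
| 40 | 10 | 0.752 | 0.621 |

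One removal fewer falls below 0.70 at every look, so the count is sensitive to a single patient. That alone does not link the drug-handling conflict to the count. The rule counts removal from the study, and Section 5.2.1.2 lets a patient stay on study and therapy after one agent is stopped.

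**The case against.** The best defense is that Table 4 is already the working text for pembrolizumab. Section 5.2.1.4 says to withhold according to it, and Section 5.2.1.5, the parent of 5.2.1.5.1, sends the reader back to it. The paragraph after the general sentence cites Table 4 and ties restart to meeting the administration criteria, with steroids tapered, and to the dose-reduction recommendations. On this reading the sentence only requires a hold, and Table 4 decides what follows. For item 4 that is coherent, and it stands. A reader might infer that Section 5.2.1.5.1 permits re-exposure after, say, grade 3-4 pneumonitis, or that each permanent-stop row is a separate contradiction. The documents do not support either: this is one generic sentence set against several rows, and it does not say that treatment must or may resume.

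On colitis, the limit to toxicities that qualify for re-dosing could be read as deferring to Section 5.2.1.5.1. That is possible but unstated. Nor is the Section 5.2.1.5.1 rule a flat stop, given its objective-cause exception.

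The defense does not reach hypothyroidism, where a required hold and an instruction to continue cannot be sequenced. It also leaves the endocrinopathy threshold and the lack of ranking in Section 5.9 untouched.

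A reader might also infer that the conflict changes who is counted under Section 8.2.2.1. The documents do not show this. Stopping pembrolizumab alone is not automatically removal from the study, and the rule acts by holding enrollment, which is now closed in both cohorts.

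**Conclusion.** The inconsistency is real but limited:
- grade 3-4 hypothyroidism: the instructions contradict each other;
- resumption after a grade 3-4 endocrinopathy: the thresholds differ;
- second grade 3 colitis without an objective cause: the two texts are not reconciled;
- the five permanent-stop listings: ambiguous rather than contradictory, since a hold followed by Table 4 is a fair reading.

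The conclusion assumes that the event is attributed to pembrolizumab and is of a type covered by Table 4. It matters for patient safety because sites could act differently on the same event. No numerical effect on any analysis or stopping boundary is claimed. This point takes no position on which instruction is clinically right.

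**What to change.** Reconcile Section 5.2.1.5.1 with Table 4 in Section 5.2.1.4 on three matters:
- hypothyroidism and the other endocrinopathies, including the threshold for resuming;
- second grade 3 colitis, including whether it qualifies for re-dosing under general instruction 2 and how the objective-cause exception fits;
- the events that Table 4 lists for permanent discontinuation, saying whether the general sentence is only the initial hold.

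Add one sentence stating which text governs where they differ, and make Section 5.9 refer to it. The content of each reconciled rule is for the clinical team.

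The cost is protocol wording, an amendment and a notice to sites. Sample size, endpoints and planned analyses do not change.
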